# 2. Protocol Stopping Criteria

Following its review of the DSMB Report and any other relevant data at each meeting, the COVAC-TP independent DSMB will make recommendations to the Steering Committee and the NHLBI Office of the Director regarding termination vs. continuation of the phase 2 clinical trial as noted in Table 2. These recommendations by the DSMB will consider the stopping rules and cumulative SAE profile to date and other relevant safety findings in the study, as well as trial quality and enrollment metrics. In the case of persistently poor trial enrollment metrics, the DSMB may recommend termination of the trial for futility, versus continuation of the trial with protocol modifications.

Reasons for early termination are as follow:

- Evidence of safety concerns—although stopping rules have been established as a guide, this can occur at any point during the study, based on the DSMB's review of cumulative data to date at scheduled or *ad hoc* DSMB meetings.
- Determination of futility: Evidence of persistently poor trial enrollment metrics, which cannot be (or has not been) remedied via protocol modification or other appropriate corrective action.

# Patients who Received Enoxaparin Thromboprophylaxis	Pause if # of Patients with Clinically-Relevant Bleeding				
<10	1				
10-<20	2				
20-<30	3				
30-<38	4				

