# IV. RESEARCH METHODS: SUMMARY OF STUDY RATIONALE

# A. Primary Outcome

PRIMARY SAFETY: Occurrence of clinically-relevant (i.e., major plus clinically relevant non-major [CRNM]) bleeding within 30 days.

Based upon International Society on Thrombosis and Haemostasis (ISTH) Scientific and Standardization Committee standardized definitions for pediatric trials [12], "Major bleeding" will be characterized by bleeding satisfying any one of the following criteria: 1) fatal; 2) clinically overt and associated with a decrease in hemoglobin of at least 2 g/dL in a 24 hour period; 3) clinically overt and for which blood product is administered; 4) retroperitoneal, pulmonary, or involving the central nervous system; 5) requiring surgical intervention in an operating suite.

"CRNM bleeding" definition includes any bleeding that does not fulfill the above criteria but fulfills one of the following: 1) Bleeding requiring medical or surgical intervention to restore hemostasis; 2) Bleeding for which medical attention is sought.

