# E. Description of Population to be Enrolled

#### 1. Target Enrollment

The target accrual is based on the primary endpoint (safety). The safety population is defined as all patients who received at least one dose of the enoxaparin regimen. In order to achieve adequate power and precision for determination of safety in the primary analysis (see also section G, below), the target enrollment is 38 evaluable children, from among a total of 12-15 participating sites. Participants who do not received at least one dose of the enoxaparin regimen (i.e. early termination, withdrawal of consent) will be replaced. Anticipating an 85% retention rate, we will enroll up to 45 participants. Both males and females of all races and ethnic groups are eligible for this study.

Table 1. Schedule of Assessments.

Assessment	Screening (Within 72 hours of hospital admission)	Enrollm ent Day 0	Day 1	Day 2	Day 3 *	Day 7 *	Day 14 *	Day 30 (+/- 2 days)
Informed consent		Х						
Enrollment		Х						
Full H&P	Х							
Focused H&P			Х	Х	Х	Х	Х	
Weight	Х							
CBC with platelet count	Х				Х	Х	Х	
PT and aPTT 	Х				Х	Х	Х	
Fibrinogen 	Х				Х	Х	Х	
Serum creatinine	Х				Х	Х	Х	
Urine pregnancy screen 	Х							
Research blood specimen 		Х	Х	Х	Х	Х	Х	
Anti-factor Xa level 			Х	+/- X				
SAE Monitoring			Х	Х	Х	Х	Х	Х
Bleeding event (based on focused interim H&P)			Х	Х	Х	Х	Х	Х
VTE event (based on focused interim H&P, with radiological confirmation when suspected clinically)			х	х	х	х	х	х
Telephone visit 								Х

Obtained for research purposes if not already being obtained clinically.

 For participants <20kg: (1) 3ml blue top tube and (1) 4mL CPT Tube (7mL total). For participants  $\ge$ 20kg, (1) 3mL blue top tube and (2) 4mL CPT tubes (11mL total). Research blood collection is for central research lab testing of D-dimer, Clot Formation and Lysis (CloFAL) assay, IL-6, and anti-SARS-CoV-2 IgG, as well as banking plasma, DNA isolated from the buffy coat, and peripheral blood mononuclear cells (PBMCs) for future research.

 Obtained at 4 hours after 1st or 2nd dose of enoxaparin, at initial dosage (mg/kg) and any subsequent change in dosage.

Focused, scripted assessment of symptoms of potential concern for bleeding events, VTE events, and SAEs. Refer to Manual of Operations.

\* If still hospitalized.

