# J. Data Safety and Monitoring Plan

#### 1. DSMP Summary

An independent Data and Safety Monitoring Board (DSMB) consisting of a pediatric hematologist, a pediatric critical care or hospital medicine physician, and a PhD-level

biostatistician will be established and supported via the Pediatric Data Coordinating Center at Johns Hopkins All Children's. The DSMB will convene at least quarterly throughout the trial, including interim analyses for safety monitoring, to review confidential and de-identified data. Criteria for halting enrollment pending further evaluation by the DSMB are shown in Table 2, below. At that time, the DMSB will consider a recommendation to terminate versus continue the trial, based on evaluation of most up-to-date literature on the rate of clinically-relevant bleeding among children hospitalized with COVID-19 outside of the trial.

A Medical Safety Officer (MSO) will function for additional safety oversite for the Overall PI, and to facilitate timely sponsor-level SAE review and communication with the DSMB. The MSO will perform an independent determination of each SAE that has been locally determined by the responsible site PI, regarding relatedness to study intervention. If EITHER determination is that the SAE is "related", the SAE will be reported to the DSMB chair. Reporting timelines are provided in the Manual of Operations

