# **Table 2.**Optimized Boundaries for Halting Enrollment (i.e., "Pause")Pending Further Evaluation by the DSMB.

#### 3. SAE Reporting Plan

SAEs will be collected from time of enrollment to the end of the 30 day study window. Diseases or conditions that were present prior to the time of randomization should not be counted as adverse events unless they increase in grade or severity during the timeframe described above.

*Adverse event:* Any untoward medical occurrence associated with the use of a drug in humans, whether or not considered drug related.

*Serious adverse event:* An adverse event is considered "serious" if, in the view of either the investigator or sponsor, it results in any of the following outcomes:

- Death
- A life-threatening adverse event
- Inpatient hospitalization or prolongation of existing hospitalization
- A persistent or significant incapacity or substantial disruption of the ability to conduct normal life functions
- A congenital anomaly/birth defect
- Important medical events that may not result in death, be life-threatening, or require hospitalization may be considered serious when, based upon appropriate medical judgment, they may jeopardize the patient or participant and may require medical or surgical intervention to prevent one of the outcomes listed in this definition. Examples of such medical events include allergic bronchospasm requiring intensive treatment in an emergency room or at home, blood dyscrasias or convulsions that do not result in inpatient hospitalization, or the development of drug dependency or drug abuse.

All SAEs will be reported within 24 hours of knowledge of the event. Please refer to the Manual of Operations for SAE reporting forms and guidelines.

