# 3. Adequacy of Protection Against Risks

With regard to risks of anticoagulation, participants in whom clinically-relevant bleeding develops in-patient (on enoxaparin prophylactic regimen) will receive appropriate medical attention, and those in whom bleeding develops as an outpatient (off enoxaparin prophylaxis) will be instructed to seek medical attention, as part of routine hospital discharge instructions, with re-enforcement by study personnel. However, it should be noted that this study involves standard prophylactic dosing of low-dose enoxaparin, and is therefore not anticipated to engender substantively greater bleeding risk than standard care, and is not expected to be associated with increased bleeding risk beyond 12 hours post-cessation of the in-patient low-dose enoxaparin regimen. With regard to participant confidentiality, participant identifiers will be highly limited (i.e., Health Insurance Portability and Accountability Act [HIPAA] "limited data set") in the database, and a unique study code will be used in lieu of patient names. These data will be kept for as long as necessary to conduct this and any future research and to comply with legal obligations related to research. A copy of all consent forms, which will contain participant names, will be retained in a secure and locked file in the office of the local site principal investigator. A key will be securely stored separately at the local institution from all study documents that will link the participant name to the study code. The study will be conducted under the Declaration of Helsinki and International Conference on Harmonization guidelines.

Non-English speaking families will be provided with an informed consent written in a language understandable to them and a translator provided. To the extent permissible by local IRB policy, a short form (in the patient's native language) may be used in lieu of a fully translated informed consent form.

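### Table 2 raises its pause threshold when the 10th, 20th or 30th child is dosed, so a lone late bleed in an earlier child need not trigger the automatic pause

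*Protocol*

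**What the plan says.** The DSMP Summary (Protocol IV.J.1) states: "Criteria for halting enrollment pending further evaluation by the DSMB are shown in Table 2, below". Table 2 is titled "Optimized Boundaries for Halting Enrollment". Its left column counts "Patients who Received Enoxaparin Thromboprophylaxis" and its right column is headed "Pause if # of Patients with Clinically-Relevant Bleeding": 1 while fewer than 10 are treated, 2 from 10 to under 20, 3 from 20 to under 30, and 4 from 30 to under 38.

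The table does not define receipt. The nearest definition is under Target Enrollment (IV.E.1): "The safety population is defined as all patients who received at least one dose of the enoxaparin regimen". We found no requirement that a child complete treatment, hospitalization or follow-up before counting toward the next row, and no staggering of enrolment across the 12–15 sites.

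The primary outcome (IV.A) is clinically relevant "bleeding within 30 days", and under the SAE Reporting Plan (IV.J.3) "SAEs will be collected from time of enrollment to the end of the 30 day study window". The Data Analysis Plan (IV.H) words the endpoint as bleeding during hospitalization. On either wording, the outcome is not known at the first dose.

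**The concern.** A child enters the denominator at the first dose but may contribute a bleed days or weeks later. The threshold can therefore rise while the children it was meant to cover are still at risk. Suppose child 10 is dosed on calendar day 3 and child 9 has the trial's first bleed on day 5. Ten children have been dosed, the row requires two bleeds, the count is one, and the table does not call a pause. Had the same bleed come before child 10 was dosed, it would have. The difference lies in how children are counted, so faster reporting does not remove it.

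Bleeding safety is the primary objective and Table 2 is the only numerical pause trigger. Other things equal, its sensitivity falls as enrolment speeds up.

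**Working it through.** **Inputs from the documents.** Thresholds: Table 2. Sample size: 38 (IV.E.1). True rates tried: 2.6% and 11.8% (Hypothesis 1: the hypothesised incidence and its upper 90% limit) and 5.6% (IV.K.1: the cited retrospective bleeding rate under thromboprophylaxis).

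**Assumptions.** Total accrual time is 2, 4 or 9 months with random (Poisson) arrivals. Bleed times are uniform over a lag of 7, 14 or 30 days from dosing. A bleed after the last child is dosed cannot pause enrolment.

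**1. The plan's own figure.** The boundaries cannot be reproduced, because the protocol gives no design rate, error level or pause probability for them.

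**2. Benchmark with every outcome known at once.** Let X(n) be the number of bleeds among the first n children dosed. Thresholds are constant within a row and counts never fall, so

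P(pause) = 1 − P[X(9)=0, X(19)≤1, X(29)≤2, X(37)≤3].

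At 5.6%, P[X(9)=0] = 0.944^9 = 0.595. Given that, split the no-pause probability by the number of bleeds among children 10–19:
- none: 0.548
- one: 0.289

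So P(pause) = 1 − 0.595 × (0.548 + 0.289) = 0.502. The same calculation gives 0.238 at 2.6% and 0.856 at 11.8%.

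**3. Weight of the first row.** P(at least one bleed in the first nine) = 1 − (1−p)^9 = 21.1%, 40.5% and 67.7% at the three rates. As a share of the whole rule this is 21.1/23.8 = 89%, 40.5/50.2 = 81% and 67.7/85.6 = 79%. The row that later dosing can switch off supplies most of the sensitivity.

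**4. How often a bleed in the first nine comes after child 10 is dosed.** By simulation:

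| Mean gap between children | bleeds within 7 days | bleeds within 30 days |
|---|---|---|
| 1 day | 38% | 83% |
| 3 days | 13% | 52% |
| 7 days | 6% | 24% |
| 14 days | 3% | 12% |

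For scale, 38 children in 2, 4 or 9 months is a mean gap of about 60/38 = 1.6, 120/38 = 3.2 or 270/38 = 7.1 days.

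**5. Pause probability as written.** At least 8,000 simulated trials per cell; where repeat runs did not agree to the point, the range is shown.

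| Scenario | 2.6% | 5.6% | 11.8% |
|---|---|---|---|
| Benchmark, outcomes known at once | 24% | 50% | 86% |
| 9 months, bleeds within 7 days | 23% | 48–50% | 84–85% |
| 4 months, within 14 days | 19–20% | 43–46% | 81% |
| 2 months, over 30 days | 8–9% | 23–24% | 60–61% |

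**6. Same thresholds applied in dosing order.** Pause at 1 bleed among the first 9 dosed, 2 among the first 19, 3 among the first 29, or 4 among the first 37, whenever the bleed occurs. This is the event in step 2, so it matches the benchmark except for bleeds that come after enrolment has closed. Simulation gave about 24%, 48–52% and 81–86%. The low end, 81% against 86%, is the 2-month, 30-day case.

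**7. Counting only children who have completed the lag or have already bled.** This pauses more often than the benchmark: about 40%, 67% and 92% in the 2-month, 30-day case.

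**The case against.** Four points can be made for the plan.

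- **Other safeguards exist.** A reader might infer that a late bleed among the first nine goes unreviewed. The documents do not support that. Clinically relevant bleeds are SAEs of particular interest, reported within 24 hours of knowledge. If either the site investigator or the Medical Safety Officer judges one related, it goes to the DSMB chair. The DSMB may act at any time, and Table 2 is described as a guide. This stands: what is lost is the automatic trigger, and only while the total count stays below the new threshold. A second affected child while 10–19 have been dosed still triggers it.
- **The large losses need assumptions that the protocol partly contradicts.** Dosing is inpatient only, and the regimen "is not expected to be associated with increased bleeding risk beyond 12 hours post-cessation of the in-patient low-dose enoxaparin regimen" (IV.K.3). No accrual period is stated. With bleeds within 7 days, the as-written rule gives about 46% and 84% at true rates of 5.6% and 11.8% over 4 months, and about 44% and 81% over 2 months. This stands, and it rules out presenting the 60% figure as the expected behaviour. The fast case cannot be dismissed either: the Background sets out to run the trial rapidly, and Table 1 plans inpatient visits to day 14.
- **The benchmark is ours.** A reader might infer that Table 2 fails its design specification. No specification is given, so no such failure can be shown.
- **Dosing order is a different counting rule.** It would pause for one late bleed in an early child even with 30 dosed and no other bleed (1/30 = 3.3%, near the hypothesised 2.6%). That is a real cost, and the sponsor and DSMB should weigh it.

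**Conclusion.** The point holds for the automatic trigger. Read literally, Table 2 moves to a higher threshold on dosing alone, and a lone later bleed in one of the first nine children then leaves the count below it. The conclusion rests on reading receipt as at least one dose. The table does not say so, but IV.E.1 supports that reading and nothing supports another.

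The loss against the benchmark depends on two quantities the documents do not give. It is about 0–2 percentage points with nine-month accrual and bleeds within a week. It is about 4–7 points at 2.6–11.8% with four months and 14 days. With two months and 30 days it is about 15 points at 2.6% and 25–27 points at 5.6% and 11.8%. The short-lag end is closer to the protocol's own view of bleeding risk. A cheap correction is still worth making in a trial whose primary endpoint is bleeding.

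**What to change.** Add a note to Table 2, leaving its thresholds unchanged: each row applies to children in dosing order (1 bleed among the first 9 dosed, 2 among the first 19, 3 among the first 29, 4 among the first 37), whenever the bleed occurs. State the resulting pause probabilities at 2.6%, 5.6% and 11.8%, with the accrual and timing assumptions behind them.

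If the sponsor and DSMB prefer to count only children who have completed a stated observation period or have bled, the note should say so, give the period and report that rule's higher pause probabilities.

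The cost is a short amendment and more pauses for DSMB review, some for a single late bleed in an early child. Under dosing order the total chance of a pause at the hypothesised 2.6% is up to about 24%, which the table already implies when outcomes are known at once. A pause leads to review, not automatic termination.

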barcode, with the association between the barcode and the participant's unique study ID maintained in the Biorepository's secure, web-based, password-protected Lab Information Management System (LIMS) maintained behind the information technology firewall at Johns Hopkins All Children's Hospital. Biospecimens will be used to identify and validate putative prognostic biomarkers in pediatric venous thrombosis and COVID-19-related illness. The genetic investigations will involve candidate genes, a genomewide association study (GWAS), and whole genome sequencing approaches in deoxyribonucleic acid. The Johns Hopkins All Children's Pediatric Biorepository uses a secure database to store all data related to the samples, behind the institutional firewall. Following completion of the protocol-specified aims, external requests for specimens in the COVAC-TP trial biobank will be vetted and made available through the National Institutes of Health (NIH), in accordance with NIH policies on data and biospecimen sharing. The second procedure will be obtaining a contrast enhanced computed tomography scan of the chest within 24 hours preceding discharge from the hospital (if not already obtained clinically during hospitalization) to assess for pulmonary emboli. Throughout their study participation, up to and including visit 6, patients will be assessed for bleeding and VTE events by their inpatient medical provider team with any SAEs being documented in the case report forms (supported by source documentation in the patient's electronic medical record) and reported to the Medical Safety Officer (MSO) as described in Section J.2. The MSO will perform an independent determination of each SAE that has been locally determined by the responsible site PI, regarding relatedness to study intervention. If EITHER determination is that the SAE is "related", the SAE will be reported to the DSMB chair. The DSMB will then assess whether any action is needed, depending on the nature of the SAE. Adverse events (and symptoms of concern for possible VTE or clinically-relevant bleeding) will be further assessed at a long-term follow up visit 30 days (+/- days) after enrollment via telephone call from a study team member.

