#### Bleeding Events:

- Major bleeds and clinically-relevant non-major (CRNM) bleeds will be considered SAEs of particular interest (if they occur during the AE reporting window).
- Based upon ISTH standardized definitions for pediatric trials [10], "Major bleeding" will be characterized by bleeding satisfying any one of the following criteria: 1) fatal;
  2) clinically overt and associated with a decrease in hemoglobin of at least 2 g/dL in a 24 hour period; 3) clinically overt and for which blood product is administered;
  4) retroperitoneal, pulmonary, or involving the central nervous system; 5) requiring surgical intervention in an operating suite.
- "CRNM bleeding" definition includes any bleeding that does not fulfill the above criteria but fulfills one of the following: 1) Bleeding requiring medical or surgical intervention to restore hemostasis, but not in an operating suite; 2) Bleeding for which medical attention is sought.

VTE events will be considered outcome events rather than SAEs, unless they otherwise fulfill the regulatory definition of an SAE (i.e., they will not fulfill the SAE criterion of investigator-defined "important medical events").

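### With 10 to 37 children dosed, a fatal or CNS bleed that leaves the pooled count below 2, 3 or 4 does not trigger the Table 2 enrolment pause, and no text seen holds enrolment while it is reviewed

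*Protocol*

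**What the plan says.** **The pause rule.** Protocol IV.J.1 states: "Criteria for halting enrollment pending further evaluation by the DSMB are shown in Table 2, below". Table 2 in IV.J.2 sets the boundary on "Pause if # of Patients with Clinically-Relevant Bleeding", by number of children dosed:

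| Dosed | Patients with a bleed needed to pause |
|---|---|
| <10 | 1 |
| 10 to <20 | 2 |
| 20 to <30 | 3 |
| 30 to <38 | 4 |

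The count pools major and clinically relevant non-major (CRNM) bleeding (IV.A and IV.J.3, Bleeding Events). Fatal and CNS bleeds are criteria of major bleeding. At the other end, the second CRNM criterion reads "2) Bleeding for which medical attention is sought". Each adds one patient.

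**The other routes for a single grave event.**
- IV.J.3: "Major bleeds and clinically-relevant non-major (CRNM) bleeds will be considered SAEs of particular interest", and "All SAEs will be reported within 24 hours of knowledge of the event".
- IV.C and IV.J.3: bleeding endpoints and all deaths are centrally adjudicated. No relatedness condition is attached.
- IV.J.1: the site investigator and the Medical Safety Officer each judge relatedness. "If EITHER determination is that the SAE is 'related', the SAE will be reported to the DSMB chair".
- IV.F: "The DSMB will then assess whether any action is needed, depending on the nature of the SAE".
- IV.J.2, on ending the trial early for safety: "although stopping rules have been established as a guide, this can occur at any point during the study". Ad hoc DSMB meetings are foreseen.
- IV.J.5: an event that qualifies as an unanticipated problem goes promptly to the overall principal investigator and the coordinating center, and also to the IRB.
- IV.F, Off-Study Criteria: the sponsor, IRB or another regulatory body can discontinue the study.

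The SAP contains no pause or stopping rule.

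**The concern.** A count that rises with the number dosed is sensible for watching a pooled bleeding rate. It responds poorly to one catastrophic event. With 9 children dosed, one bleed for which attention was merely sought stops enrolment. With 10 dosed, a fatal bleed with no earlier bleed on the count does not. It falls 1 short of the boundary at 10 to 19 dosed, 2 short at 20 to 29 and 3 short at 30 to 37.

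What is at stake is participant protection. Further children could be enrolled and dosed while the first grave bleed is still under review. Neither the primary estimate nor its confidence interval is affected. A smaller point is that individual notice to the DSMB chair depends on a relatedness judgement, which Table 2 does not require and which can be difficult in a very ill child.

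**Working it through.** **1. The plan's own figure.** The boundaries are called optimized, but no target rate, error level or formula is given. They can be read but not re-derived.

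**2. Inputs.**
- Boundaries c(n) = 1, 2, 3, 4, from Table 2.
- Children n = 1 to 37. The target is 38 dosed and only undosed children are replaced (IV.E.1), so at 38 nothing is left to pause.
- Total bleed rate T = 5.6% (IV.K.1, retrospective data in hospitalized children on thromboprophylaxis) or 2.6% (Hypothesis 1, IB).
- Rate g of fatal, CNS or otherwise life-threatening (grave) bleeds, included in T. The documents give none, so 0.25%, 0.5% and 1% are **assumed**.
- Children are treated as independent and each bleed is counted at once.

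**3. Formula.** Let P_n(G, B) be the probability of having G grave and B total bleeds after n children with no pause so far:

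P_n(G, B) = (1 − T)·P_{n−1}(G, B) + (T − g)·P_{n−1}(G, B−1) + g·P_{n−1}(G−1, B−1),

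removing every state with B ≥ c(n). The answer is the sum of P_37(G, B) over G ≥ 1.

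**4. Checks by hand.**
- A pause within the first nine children has probability 1 − (1 − T)^9: 1 − 0.944^9 = 40.5% and 1 − 0.974^9 = 21.1%. Both agree with the recursion.
- The simplest case is that the only bleed in children 1 to 37 is grave and falls at child 10 to 37. Its probability is 28·g·(1 − T)^36. With g = 0.5%: 28 × 0.005 × 0.974^36 = 5.4%, and 28 × 0.005 × 0.944^36 = 1.8%. The rest of the totals below comes from runs with two or three bleeds that stay under the boundary.

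**5. Chance of at least one grave bleed and no Table 2 pause.**

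| Assumed g | T = 5.6% | T = 2.6% | Grave share of all bleeds (g/T) |
|---|---|---|---|
| 0.25% | 2.65% | 4.68% | 4% / 10% |
| 0.5% | 5.20% | 9.14% | 9% / 19% |
| 1% | 10.00% | 17.39% | 18% / 38% |

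The 17% cell makes 38% of all bleeds grave. That is implausible when IV.K.1 says minor bleeds outnumber major ones. The main range is therefore the first two rows, about 3% to 9%. If a bleed is counted only after five more children have been dosed (assumed), the first two rows become 4% to 5% and 7% to 10%.

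**6. Exposure.** When a first grave bleed is counted at child n without a pause, 38 − n children remain: 28 at n = 10 and 1 at n = 37, averaging about 15 (14.5 to 15.2). That is a ceiling. The number dosed during a review cannot be computed, because neither accrual rate nor review time is given.

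**7. When a first grave bleed does pause enrolment.** Earlier bleeds stay on the count. Suppose the trial resumes after any earlier pause. A first grave bleed at child n = 10 to 37 then reaches the boundary if at least c(n) − 1 of the earlier n − 1 children had a non-grave bleed, each with probability (T − g)/(1 − g). Averaged over n, this happens in 34% to 39% of cases at T = 5.6% and 10% to 15% at T = 2.6%.

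**The case against.** The strongest reply is that count-based pausing backed by DSMB discretion is a coherent design, and that nothing in the protocol promises a hold for a single event. Notice within 24 hours is required, and one related call from either assessor is enough to alert the chair. A fatal or CNS bleed on an anticoagulant would escape that notice only if both assessors called it unrelated, which the documents give no reason to expect. The DSMB can then act on the nature of the event, and the IRB route in IV.J.5 carries no relatedness condition. Every grave-bleed rate used here is assumed, and the harm itself, children dosed during review, cannot be measured. All of this stands. It makes the point a minor one, but it does not supply a hold: each of these routes gives notice, review or discretionary action.

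Three stronger readings are tempting and not supported:
- *No first grave bleed after the tenth child can pause enrolment.* It can when earlier bleeds are on the count (step 7).
- *A single fatal bleed would go unreviewed.* The routes listed above show otherwise.
- *No hold exists anywhere.* The Manual of Operations, cited for reporting timelines and SAE guidelines, and the adjudication charter were not available. IV.J.1 does, however, place the halting criteria in Table 2.

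**Conclusion.** The point holds in a narrow form. In the documents seen, a grave bleed counted with 10 to 37 children dosed does not pause enrolment if it is the only counted bleed or leaves the cumulative count below 2, 3 or 4. No text shown holds enrolment during the review that follows. That reading comes directly from Table 2 and needs no assumption.

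Its size does need assumptions. At grave-bleed rates of 0.25% to 0.5%, with total rates of 2.6% to 5.6%, independent children and immediate counting, the chance is about 3% to 9%. A reader might take this as the chance that children are exposed without oversight. It is only the chance that a grave bleed occurs and no automatic pause follows. This is a minor improvement in participant protection, not an error in the analysis.

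**What to change.** Add one line to Table 2: any fatal, CNS or otherwise life-threatening bleed in a dosed child, whatever its assessed relatedness, pauses enrolment pending prompt ad hoc review by the existing DSMB. Keep the composite counts. Leave other major bleeds, such as a 2 g/dL hemoglobin fall or a blood product given, on the existing SAE path. If the Manual of Operations already contains such a hold, a cross-reference from Table 2 is enough.

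The cost is one protocol sentence and an occasional short pause. The chance that the line is triggered at least once in children 1 to 37 is 1 − (1 − g)^37: 9%, 17% and 31% at g = 0.25%, 0.5% and 1%. In some of those runs Table 2 pauses anyway. Runs paused only because of the new line are those in step 5: 3% to 5%, 5% to 9% and 10% to 17%. The change works only while enrolment is open. SAP 2.5 already reports 38 enrolled, so for this trial it serves mainly as a lesson for the next protocol.
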